- Those with a negative urine culture will not be prescribed antibiotics and will be followed per protocol.
- Those with a positive urine culture who *report persistent UTI symptoms* will be given antibiotics following the priority list above with consideration to reported antimicrobial sensitivities.
- Those with a positive urine culture who *report resolution of UTI symptoms* will not be given antibiotic

Empiric Antibiotic Treatment.

- Those with a negative urine culture will be told to stop antibiotics
- Those with a positive urine culture sensitive to the empiric antibiotic will be instructed to complete the full course of their antibiotics
- Those with a positive culture resistant to empiric antibiotic will be given an alternative antibiotic per antibiotic protocol and will be followed per protocol. If there are no oral antibiotic options with patient-specific and antimicrobial sensitivities, we will engage local infectious disease physicians for management as per standard clinical protocols.

[figure not shown]
D.1.6. Study follow-up assessments.

All participants will be followed with electronic surveys via Research Electronic Data Capture (REDCap) software, which is a browser-based, metadata-directed EDC software and workflow methodology for designing

clinical and translational research databases,⁷² on day 2-3 (after result of urine culture). To avoid limiting enrollment to only those with access to technology, our research coordinator can also call and administer the questionnaire by phone to ensure ability to access and complete electronic materials. Follow-up assessments will be completed weekly for a total of 4 weeks. These will include UTISA questionnaire,⁶⁸ antibiotic associated side effects, use of other symptom mitigating remedies, and adherence to assigned study arm.

Participants will be provided with a clinical line to call 24/7 with report of worsening symptoms which will be discussed with the PI, [name] for determination of antibiotic prescription and if participants report fevers or chills this will prompt an in-person evaluation in clinic during business hours or the emergency department after hours. If participants call to report new symptoms during the study course, a repeat urine culture will be obtained.⁷³ Given that these episodes could be considered either a recurrent or incompletely treated infection we plan to manage these per clinical care and not based on the participants initial study arm.

Figure 2: Study Flow Diagram

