For a larger trial, electronic surveys may significantly reduce research coordinator burden. To evaluate feasibility of this approach we will administer electronic surveys through Research Electronic Data Capture (REDCap) software.⁷² Surveys are sent via email and can be accessed through either a laptop, desktop or smart phone. Participants will also be called at day 2-3 (after urine culture results) and then weekly to assess issues with electronic materials. We will evaluate proportion of those with electronic success and investigate demographic variables that may be associated with inability to utilize electronic materials. To assess patient adherence to study procedures, defined as completion of all follow-up questionnaires, we will describe the percentage of enrollees who completed 100% of study procedures, 80% to 100% of study procedures and 50% to 80% of study procedure. A priori, we believe that compliance with 70% of study procedures will demonstrate satisfactory patient adherence to protocol. If the underlying adherence rate is 70%, a sample size of 70 provides a 10.1% MoE.

Exploratory Aim: To explore the safety of a culture-directed UTI treatment strategy and preliminary secondary outcomes of assigned treatments.

Safety Aims⁶²

1. Adverse events per group (most likely antibiotic side effects (i.e., gastrointestinal distress, antibiotic related diarrhea, rash) between groups.
2. Serious adverse events per group (defined in line with FDA reporting guidelines as a medical event that does one or more of the following: results in death, is life - threatening, requires inpatient hospitalization or prolongation of existing hospitalization, results in persistent or significant disability/incapacity, or is a congenital anomaly/birth defect.⁷⁷

Analysis. We anticipate that adverse events will be reported relatively infrequent.⁷⁸ All outcomes will be described using numbers and proportions of patients. Proportions between groups will be compared with either chi-square or Fischer's exact testing.

Secondary exploratory aims.

Proportion of those with clinical cure (as 2 or less points (slight, very slight, or no problems) on all five components of the UTISA (ref) at day 14 (***future trial primary outcome***)

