Analysis. All outcomes will be described using numbers and proportions of patients or means with confidence intervals. Proportions between groups will be compared with either chi-square or Fischer's exact testing and means will be compared with student's t-testing. Exploratory logistic regression modeling will be utilized to investigate the odds of both initial treatment failure and/or recurrent of UTI symptoms between groups and based on baseline characteristics

Power analysis:^{76,79} As above, we propose a future trial with a primary outcome to be symptom resolution at day 14 defined as 2 or less points (slight, very slight, or no problems) on all five components of the UTI symptom assessment (UTISA).^{43,78} The literature suggests 58-80% of women receiving empiric antibiotics for patient reported UTI will achieve clinical cure by day 3-7 after treatment initiation.^{43,78} Given that only women

with a positive urine culture will be given culture-directed antibiotics, and women in the empiric arm may have to have their antibiotics changed or stopped at the time of culture result, we anticipate a higher proportion of those in the culture-directed arm to have symptom resolution at day 7. Assuming 70% symptom resolution in the empiric arm, a future trial of 262 participants, with 131 per arm, would have 80% power to detect a 15-percentage point difference between groups with a 2-sided alpha of 0.05, while a sample size of 300 would be required assuming 65% resolution. Therefore, we believe that successfully recruiting a total of 70 participants at a rate of 6-7 participants/month will confirm the feasibility of future trial completion in <4 years (equivalent to other trials of antibiotic regimens for symptomatic UTI).^{17,78}

Statistical methods

Primary Outcomes	Statistical analysis
Feasibility: 
 - Number of subjects that were screened for participation - Number and proportion of subjects screened who met inclusion/exclusion criteria - Number and proportion of subjects who either declined participation or were ineligible (including reasons for ineligibility) - Number and proportion of eligible subjects that were enrolled in the study - Number and proportion of subjects enrolled who completed the study - Monthly enrollment rate 	Descriptive analysis = counts and proportions or means with standard deviation

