Adherence: 
 - Number of those that completed all study procedures - Number of subjects that took alternative agents taken by subjects for management of symptoms - Number of subjects in the culture-directed arm that acquired off-protocol antibiotics for their symptoms - Number of subjects able to complete electronic surveys 	Descriptive analysis = counts and proportions
Secondary Outcome	
Proposed primary outcome for future trial (Clinical Success at 14 days UTISA 1-3,5<=1)	Descriptive analysis = counts and proportions Comparative = Chi-square

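### The day-14 UTISA outcome, the future trial's proposed primary, has a cut-off of 2 in the text and 1 in the Statistical methods table

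*Combined protocol and SAP*

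**What the plan says.** The outcome is described in three places, each time at day 14 and each time as the future trial's primary outcome.

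- **Under the Secondary exploratory aims heading in D.1.7**, the outcome reads: "Proportion of those with clinical cure (as 2 or less points (slight, very slight, or no problems) on all five components of the UTISA".
- **D.1.7, Power analysis:** "symptom resolution at day 14 defined as 2 or less points (slight, very slight, or no problems) on all five components".
- **Statistical methods table, Secondary Outcome row:** "Proposed primary outcome for future trial (Clinical Success at 14 days UTISA 1-3,5<=1".

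A between-arm comparison of this outcome is planned both in the analysis text that follows the exploratory aims and in the table.

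The Power analysis paragraph also sizes the future trial. It cites literature in which "58-80% of women receiving empiric antibiotics for patient reported UTI will achieve clinical cure by day 3-7" and then states: "Assuming 70% symptom resolution in the empiric arm, a future trial of 262 participants, with 131 per arm", for 80% power to detect a 15-point difference at two-sided alpha 0.05, "while a sample size of 300 would be required assuming 65% resolution". The direction of the expected effect is given for another day: "we anticipate a higher proportion of those in the culture-directed arm to have symptom resolution at day 7". On timing, D.1.6 says "Follow-up assessments will be completed weekly for a total of 4 weeks", in addition to a survey at day 2-3.

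**The concern.** The text sets the threshold at 2 on all five components. The table sets it at 1 and appears to apply it to items 1, 2, 3 and 5 only. Instrument, day and role are the same, and nothing in the document says which statement governs.

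Two things are at stake. First, an analyst following the plan could compute either success rate and either between-arm test, and could choose between them after seeing both. Second, a pilot should hand the definitive trial a settled endpoint and a usable planning rate. Here the proposed primary endpoint is itself ambiguous, and the future sample size depends on its rate.

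A smaller loose end lies in the same paragraph: the outcome is defined at day 14, but the expected advantage is stated for day 7 and the literature range is for days 3-7. Day 7 appears only in that expectation, so it is not a third definition. It does leave unclear which day the 70% and 65% planning rates refer to.

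**Working it through.** **1. The definitions side by side**

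| Place | Cut-off | Components | Day |
|---|---|---|---|
| Secondary exploratory aims | at most 2 | all five | 14 |
| Power analysis | at most 2 | all five | 14 |
| Statistical methods table | at most 1 | 1-3 and 5, as printed | 14 |

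**2. Do the rules classify women differently?**

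- *Score 2 on every component:* success under the text, failure under the table. This holds whichever items the table's shorthand denotes.
- *Score 3 on item 4, 0 elsewhere:* failure under the text, success under the table, if the shorthand means items 1, 2, 3 and 5. The document does not number the UTISA items, so this case rests on that reading.

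If only the cut-off differs, every success under the table rule is also a success under the text rule, so the table rate cannot be the higher one. If an item is also dropped, neither rule contains the other and the rate could move either way.

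**3. Size in the pilot**

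Inputs: 70 women and 1:1 allocation (D.1.1), so 70/2 = 35 per arm. Equal arms and complete day-14 data are assumed.

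- One woman reclassified moves her own arm's rate by 1/35 = 2.9 points.
- The between-arm difference shifts by (net reclassified in one arm − net in the other)/35. A net of 0 gives 0, a net of 1 gives 2.9 points, and a net of 3 gives 8.6 points.
- 95% half-width of the difference at 70% v 85%: 1.96 × √[(0.70×0.30 + 0.85×0.15)/35] = 19.2 points.
- At 65% v 80%: 1.96 × √[(0.65×0.35 + 0.80×0.20)/35] = 20.6 points.

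**4. Size in the future trial**

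The plan's own totals reproduce. Exact power of Fisher's exact test is 80.1% with 131 per arm at 70% v 85%, and 80.3% with 150 per arm at 65% v 80%. The sample-size arithmetic is therefore not at fault.

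Those totals show how N responds to the assumed rate: 300 − 262 = 38 women, and 38/262 = 14.5%, for a rate 5 points lower with the 15-point difference held fixed. The Power analysis paragraph also concludes that the future trial could finish in under 4 years at 6-7 participants a month. At 6 a month, 262/6 = 43.7 months but 300/6 = 50 months, beyond 48. At 7 a month, 300/7 = 42.9 months.

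No corrected N follows, because the document gives no success rate specific to either rule.

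**The case against.** The strongest reply is that this is probably a slip in one table cell. The text rule appears twice with response labels, the outcome is exploratory, and with a half-width of about 19 points neither rule supports a firm inference from the pilot. The future trial will have its own protocol in which to settle the definition. A slip is indeed plausible, which is why the text rule is the default below. But the table is current text and states the analysis of this outcome, so the contradiction stands until someone removes it.

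Other points, and what remains of them:

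- **The item set is read from shorthand.** Correct, and only the cut-off conflict is treated as certain.
- **The 14.5% is not the effect of this defect.** Correct. It measures how sensitive N is to a 5-point change in the assumed rate; nothing in the document says that switching rules moves the rate by that much, or at all.
- **The 35-per-arm figures are optimistic.** Correct; they are best case. If, for illustration, 70% of women gave day-14 data (the plan's adherence benchmark), there would be about 24.5 per arm. One woman would then be 1/24.5 = 4.1 points and the half-width at 70% v 85% about 23 points.
- **The weekly schedule is not anchored.** Neither D.1.1 nor D.1.6 says whether weeks run from day 0 or from the culture result. Counted from day 0, days 7 and 14 are both survey days; counted from day 2-3, surveys fall near days 9-10 and 16-17. A day-14 outcome suggests the former, but the text does not say so.
- **Shared citations do not settle the rule.** The same references follow the text definition and the 58-80% range. This leans towards the text rule but does not show which cut-off those sources used.

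**Conclusion.** The concern holds and should be fixed. The conflict between cut-offs of 2 and 1 is on the page and does not depend on how the item shorthand is read; the apparent loss of one component is likely but unconfirmed. Followed as written, the plan yields two success rates and two between-arm comparisons for one stated outcome.

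The consequences for the pilot are limited. Recruitment, adherence and the sample size of 70 do not change, and the number of women classed differently cannot be derived from the document. The larger consequence is for the future trial, whose proposed primary endpoint and planning rate both rest on a definition that the plan gives in two incompatible forms.

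**What to change.** Before any outcome data are analysed, state one cut-off, one item set (items named, not only numbered) and one time point, and use them identically in the Secondary exploratory aims, the Power analysis paragraph and the Statistical methods table.

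- **Default:** keep the text rule (all five components at most 2, day 14) and correct the table cell to match. If the other rule is wanted, report it only as a labelled sensitivity analysis.
- **If the table rule was intended:** change the two text definitions instead, and recheck the 70% and 65% planning rates against that rule.
- **In either case:** reconcile the day-7 expectation in the Power analysis paragraph with the day-14 definition, and say which day the planning rates refer to.

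The cost is one table cell, or two sentences if the table rule was intended, plus one clause on timing. No new data are needed.
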